The PrEvention of post-traumatic contractuRes with Ketotifen I (PERK-I) trial, a Phase II singlecenter randomized clinical trial (RCT) that compared oral Ketotifen Fumarate to a lactose placebo showed that Ketotifen Fumarate was neutral in terms of improving elbow range of motion (ROM)⁶. However, a subgroup of the trial, i.e., those who underwent surgery, indicated that Ketotifen Fumarate improved their range of motion. Therefore, the PrEvention of posttraumatic contractuRes with Ketotifen 2 (PERK-2) trial will assess the effectiveness of Ketotifen Fumarate in increasing the range of motion among surgical patients.

2. Study Objectives

The PERK-2 study aims to demonstrate that Ketotifen Fumarate (2 mg or 5 mg) administered within 10 days of injury is more effective than a placebo in reducing post-traumatic elbow joint contractures in adult participants with elbow fractures and/or dislocations. The efficacy of Ketotifen Fumarate over placebo will be assessed by comparing the difference in elbow range

Patient-Reported Outcome Measures (PROM). Lastly, the study will assess the safety of Ketotifen Fumarate through the reporting of adverse events (AE) and serious adverse events (SAE), fracture healing, and heterotopic ossification (HO) formation.

3. Study design

The PERK-2 trial is a phase III randomized controlled multicentre trial with three parallel groups. Eligible participants were assigned to receive Ketotifen Fumarate 2 mg, Ketotifen Fumarate 5 mg, or a lactose placebo in a 1:1:1 ratio. Eligible participants will be recruited at fifteen centers across North America.

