3.1. Treatment Allocation/Randomization

Randomization will be centralized, secured, and concealed via a computer-generated randomization scheme to prevent allocation bias. The randomization criteria will be reviewed and approved by an independent Biostatistician. Screening, randomization, and enrolment will be organized through the Epidemiology Coordinating and Research Centre (EPICORE) at the University of Alberta. Eligible participants will be assigned to Ketotifen Fumarate 2 mg, Ketotifen Fumarate 5 mg, or lactose placebo in a 1:1:1 ratio. A computer generated randomization scheme stratified by site with block sizes of 3:6:9 will be used to assign eligible participants. The Investigators will have access to the randomizer (on REDCap) over the Internet via a desktop computer or a web-enabled smartphone.

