3.3. Concomitant Care

Participants will receive the following care while taking trial medication.

- a) Surgery: The participant and surgeon will determine the type of operation. This management is not randomly assigned and is determined by injury characteristics. The operation can be performed before or after randomization; randomization must occur within 10 days of injury.
- b) Medications: Analgesia can be provided by acetaminophen, opioids, and/or nonsteroidal anti-inflammatory drugs (NSAID) as required. The NSAIDs may have a confounding effect on the ROM measures by preventing HO following elbow injuries. Heterotopic ossification (HO) refers to bone formation in soft tissue. NSAIDs may be used in this trial as an analgesic at the discretion of the participant and surgeon because of the known analgesic benefits for

musculoskeletal injury and the ubiquitous accessibility to NSAIDs with non-prescription preparations.

lberta Health

c) Rehabilitation/Splints: If possible, at the site, a physiotherapist will direct a standardized home exercise program (HEP) for all groups. The HEP will consist of active ROM exercises for elbow extension-flexion arc and forearm pronation-supination arc performed 3x/day with 20 repetitions. Visits to the physiotherapist every 2 weeks will monitor progress and reinforce adherence to home therapy. Stretching splints will be used when physiotherapy alone is insufficient, which occurs at least 12 weeks post-randomization.

4. Sample Size Determination

The sample size was estimated using the Analysis of Covariance (ANCOVA) model using the mean difference of injured and contralateral elbow extension-flexion arc ROM at Week 12. The sample size was calculated based on a mean difference of 15° in the extension-flexion range of motion and a standard deviation of 45° between participants who received 2 mg or 5 mg Ketotifen Fumarate and those who received a placebo, using 95% power and a two-sided test at the 0.05 α -level. The sample size was recalculated due to COVID-19 (which temporarily impacted enrolment) and budgetary constraints. A total sample size of 381 participants (127 participants per arm) was determined to be adequate based on a mean change of 10° extension-flexion arc ROM from baseline to week 12 and a standard deviation of 25°, assuming an overall dropout rate of 11%. The standard deviation used was obtained from PERK-1 trial data. Following permission from Health Canada, the sample size was increased to 395.

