7.1. Descriptive Analysis

Continuous endpoints will be summarized using means, standard deviation, medians, and interquartile ranges. The differences among groups will be compared using Kruskal-Wallis's test. Categorical endpoints will be summarized using frequency and proportion. Chi-square tests will be used to compare categorical endpoints. Point estimates with two-sided 95% confidence intervals will be produced for group differences. These endpoints, baseline covariate, and stratification factors used during randomization will be summarized by treatment intervention

for the ITT population. Similar analyses will be conducted for the PP population and safety population.

Alberta Health

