7.2. Primary, secondary, and safety analyses

The linear regression model will be used to model the mean differences in the range of motion as a function of the intervention received. The unadjusted model will use a univariate linear regression model to assess whether the participants' means of range of motion received Ketotifen Fumarate (2 mg or 5 mg) differed from those who received lactose placebo. A multivariate regression model will be used to adjust for the effect of baseline covariates, i.e., sex, age, side of injury is the same as the dominant hand, type of elbow injury, concurrent injury and site as a random variable. Type of elbow injury is defined as AO/OTA classification, i.e., distal humerus vs. proximal radius and ulna. Table 2 summarizes the statistical analyses.

Table 2: Statistical Analysis of Primary, Secondary, and Safety Endpoints

| Study Endpoint | Statistical Model | Estimate of treatment effects |
|--|--|---|
| | | |
| The mean difference between | Linear regression | The unadjusted mean difference |
| injured and contralateral elbow | This model will be used to obtain the unadjusted mean | and the corresponding 95% |
| flexion-extension at Week 12 | difference between the injured and contralateral elbow | confidence intervals |
| | flexion-extension at Week 12. | |
| | Secondary | |
| The mean difference between injured and contralateral flexion at Week 12 | The data will be analyzed with or without adjusting for specific baseline covariates. The statistical models are described below: a) Linear regression model This model will be used to obtain the unadjusted mean difference between injured and contralateral flexion at Week 12. b) The mixed-effects linear regression model This model will be used to obtain the adjusted mean difference between injured and contralateral flexion at Week 12. b) The mixed effects linear regression model This model will be used to obtain the adjusted mean difference between injured and contralateral flexion at Week 12. The baseline covariates sex, age, side of injury is the same as the dominant hand, type of elbow injury, and concurrent injury will be regarded as fixed variables, and site as a random variable. Type of elbow injury is defined as AO/OTA classification, i.e., distal humerus vs. proximal radius and ulna. | The mean difference and its corresponding 95% confidence intervals for both the unadjusted and adjusted analysis |

Alberta Health Services

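### Table 2 gives the primary endpoint only an unadjusted regression, out of line with the site-stratified randomization, the Section 7.2 text and the secondary Week 12 rows; the cost is precision, not validity

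*SAP*

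**What the plan says.** - **Randomization (Section 3.1).** "A computer generated randomization scheme stratified by site with block sizes of 3:6:9 will be used to assign eligible participants". Site is the only stratification factor named.
- **Primary row of Table 2 (Section 7.2).** One model, a linear regression: "This model will be used to obtain the unadjusted mean" difference between injured and contralateral elbow. The estimate column lists only the unadjusted difference and its 95% interval.
- **Secondary Week 12 rows of Table 2.** For flexion, extension, pronation, supination, DASH, PCS and OES: "The data will be analyzed with or without adjusting for specific baseline covariates". Each row gives the unadjusted regression and a mixed model with sex, age, injury on the dominant side, injury type and concurrent injury as fixed effects and site as random.
- **Opening text of Section 7.2.** It describes both an unadjusted and a covariate-adjusted model for range of motion, and does not confine the adjusted one to secondary endpoints.
- **Section 4.** It names ANCOVA for the primary-endpoint sample size. The recalculation rests on "a mean change of 10° extension-flexion arc ROM from baseline to week 12 and a standard deviation of 25" degrees, and later "the sample size was increased to 395".
- **Section 7.1.** The "stratification factors used during randomization will be summarized by treatment intervention", which is description only.
- **Section 7.4.** If more than 5% of primary outcomes are missing, they are imputed with the same covariates and site in the imputation model. The completed data sets are then analysed with the Section 7.2 model, in the singular.
- **Injury type.** "Type of elbow injury is defined as AO/OTA classification, i.e., distal humerus vs. proximal radius and ulna". Section 2 describes the population as "adult participants with elbow fractures and/or dislocations".

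**The concern.** The analysis that decides the trial leaves out the factor used to stratify randomization, and also leaves out covariates that the SAP already models for every other Week 12 efficacy endpoint. Stratifying by site balances the arms within site. An analysis that ignores site then leaves between-site variation in the error term, so the standard error is too large when sites differ. Omitting prognostic covariates likewise widens the interval.

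The SAP is also not of one mind. Table 2 says unadjusted only, the text above it can be read as promising an adjusted primary analysis as well, and Section 7.4 points to a single model where two are described. The 11% dropout assumed in Section 4 is above the 5% trigger for imputation, so the reference in Section 7.4 may well come into use. If the choice stays open, it could be made after results are seen.

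**Working it through.** **Inputs from the SAP.** Difference 10°, SD 25°, dropout 11%, totals 381 and 395 (Section 4); fifteen centres (Section 3); site-stratified blocks of 3, 6 and 9 (Section 3.1).

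**Assumptions.** The SAP gives no covariate R² and no site ICC, so ranges are used. The 25° is stated for a change from baseline and is taken to hold for the injured-minus-contralateral difference at Week 12. Each dose is compared with placebo at two-sided 0.05.

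**1. Reproducing 381.** Per arm, n = 2 × 25² × (1.960 + 1.036)² / 10² = 112.2, so 113. Then 113 / 0.89 = 126.97, so 127, and 3 × 127 = 381. The match needs 85% power, which the SAP does not state; 80%, 90% and 95% give 336, 447 and 552. So 381 is what an unadjusted comparison of two means needs at 85% power, with no gain from covariates.

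**2. Covariates only.** Evaluable per arm: 395 × 0.89 / 3 = 117.2, so 117. The residual SD is 25 × √(1 − R²), power comes from the noncentral t distribution, and the half-width is 1.96 × SD × √(2/117).

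| R² | Power | 95% CI half-width |
|---|---|---|
| 0 (unadjusted) | 86.1% | 6.41° |
| 5% | 87.8% | 6.24° |
| 10% | 89.5% | 6.08° |
| 20% | 92.6% | 5.73° |

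**3. Site only.** With arms balanced within site, ignoring site acts like using a critical value of 1.96 / √(1 − ICC) (normal approximation). The last two columns differ in whether site variance is added to 25² or is part of it.

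| ICC | Type I error, site ignored | Power gained by modelling site (added) | Power gained (inside 25°) |
|---|---|---|---|
| 0.02 | 0.048 | 0.4 points | 0.4 points |
| 0.05 | 0.044 | 1.1 points | 1.0 points |
| 0.10 | 0.039 | 2.5 points | 2.0 points |

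**4. Site and covariates together (simulation).** Setting: 395 randomized over 15 sites of assumed unequal size, blocks of 3/6/9 within site, 11% random dropout, five covariates, random site intercept fitted by REML, site variance added to 25². Power uses 12,000 runs (standard error 0.003) and type I error 20,000 runs (0.0015).

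| ICC / R² | Type I error, unadjusted vs mixed | Power, unadjusted vs mixed |
|---|---|---|
| 0 / 0 | 0.048 vs 0.050 | 86.2% vs 85.9% |
| 0.05 / 5% | 0.045 vs 0.050 | 85.4% vs 87.5% |
| 0.10 / 10% | 0.041 vs 0.051 | 84.3% vs 89.0% |

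A separate simulation with 339 completers, site as fixed effects and one covariate agrees in direction. At ICC 0.10 and R² 10%, type I error was 0.038 unadjusted and 0.048 adjusted, and power was 87.3% and 92.2%. Across its scenarios the unadjusted estimate averaged 9.9° to 10.1° for a true 10°, so it is unbiased.

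**5. If adjustment excluded participants.** Suppose 5% had no injury-type level and were dropped, leaving 111 per arm. At R² 5% the power is 86.1%, the same as unadjusted. With 10% dropped (105 per arm), R² must reach about 10% to break even at about 86%. Both shares are assumptions, used only to show that the gain could be cancelled.

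**The case against.** The strongest reply is that nothing is invalid. An unadjusted primary analysis is conventional, and the 381 is reproduced by an unadjusted comparison, so this analysis delivers what the trial appears to have been sized for. The benefit of adjusting depends on an R² and an ICC that the SAP does not supply. Subtracting the contralateral elbow may already remove some age- and sex-related variation. The flexion-extension arc of the injured elbow also gets an adjusted repeated-measures model elsewhere in Table 2, although that is a different quantity from the primary difference. All of this stands, and it limits the point to a recommended improvement.

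Four stronger readings are tempting, and the document does not support them:

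- *The primary test is biased or inflates false positives.* The calculations show the opposite: no bias, and a slightly conservative test when sites differ.
- *Planned power is missed.* The recalculation states no power. The 95% in Section 4 belongs to the calculation with 15° and 45°.
- *The SAP has no adjusted model for the primary endpoint, or the primary is the only unadjusted Week 12 endpoint.* The Section 7.2 text can be read as covering the primary endpoint, and the five Week 12 safety rows are deliberately unadjusted.
- *Participants will be lost because dislocations have no injury-type level.* Section 2 mentions dislocations, but the SAP does not show that dislocations without fracture are enrolled, nor how many. Section 1 says the trial concerns surgical patients.

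**Conclusion.** The point holds as a matter of efficiency and consistency. Table 2 omits the stratification factor and the planned covariates from the primary analysis, and this does not sit with the Section 7.2 text, the ANCOVA in Section 4 or the single model that Section 7.4 presumes. On the assumed ranges, adjusting adds about 2 points of power (85.4% to 87.5%) at ICC 0.05 and R² 5%, and about 5 points (84.3% to 89.0%) at 0.10 and 10%. With nothing prognostic it loses 0.3 to 0.4 points. These sizes rest on the assumed ICC, R² and site sizes, and on 25° applying to the primary endpoint. The direction of the effect is secure; its size is uncertain. The change should be made, but leaving it would not invalidate the trial.

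**What to change.** Before unblinding, and after checking what the protocol names:

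1. Put in the primary row of Table 2 the mixed model already written for the secondary Week 12 rows, by assigned arm, with the five listed covariates fixed and site random. Keep the unadjusted regression as the supportive analysis.
2. Make the Section 7.2 text agree with the table, and have Section 7.4 name that model explicitly for the imputed data.
3. If any enrolled participant fits neither AO/OTA category, add an "other" level for injury type, fixed blind, and use it in Section 7.2 and in the imputation model. Section 7.4 provides imputation only for the primary outcome, so it would not fill this covariate. Report the number analysed under both models.
4. If the protocol names the unadjusted analysis and is not amended, enter the adjusted model as a pre-specified sensitivity analysis.

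The cost is a dated SAP edit using text that already exists, and possibly a protocol amendment. The primary result would then depend on the covariate model, and under half a point of power is lost if site and covariates explain nothing.

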| The mean difference between injured and contralateral elbow supination at Week 12 | The data will be analyzed with or without adjusting for specific baseline covariates. The statistical models are described below: a) Linear regression model This model will be used to obtain the unadjusted mean difference between injured and contralateral supination at Week 12. b) The mixed-effects linear regression model This model will be used to obtain the adjusted mean difference between injured and contralateral supination at Week 12. b) The mixed-effects linear regression model This model will be used to obtain the adjusted mean difference between injured and contralateral supination at Week 12. The baseline covariates sex, age, side of injury is the same as the dominant hand, type of elbow injury, and concurrent injury will be regarded as fixed variables, and site as a random variable. Type of elbow injury is defined as AO/OTA classification, i.e., distal humerus vs. proximal radius and ulna. | The mean difference and its corresponding 95% confidence intervals for both the unadjusted and adjusted analysis |

| Study Endpoint | Statistical Model | Es | timate of treatment effects |
|-------------------------------|--|----|---|
| The mean change in flexion- | The data will be analyzed using | • | ANCOVA: The p-value. |
| extension arc of the injuired | a) Analysis of Covariance (ANCOVA) | | |
| elbow from Week 2 to Week 52 | This model will be used to assess the mean difference in flexion-extension arc between Week 2 and Week 52 among the treatment groups after adjusting for flexion-extension arc at Week 2 (baseline value). The model will have Dependent variable: The flexion-extension arc at Week 52 Independent variable: Treatment group Covariate: Flexion-extension arc at Week 2, sex, age, side of injury is the same as the dominant hand, type of elbow injury, and concurrent injury will be regarded as fixed variables, and site as a random variable. Type of elbow injury is defined as AO/OTA classification, i.e., distal humerus vs. proximal radius and ulna. | - | Mixed-effect linear regression model: The mean difference and its corresponding 95% confidence intervals |

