| | b) Mixed-effects linear regression model This model will be used to account for correlation among observations and estimate the effect of covariates on repeated outcomes. It will use the flexion- extension arc recorded at all time points. Also, the baseline covariates sex, age, side of injury is the same as the dominant hand, type of elbow injury, and concurrent injury will be regarded as fixed variables, and site as a random variable. Type of elbow injury is defined as AO/OTA classification, i.e., distal humerus vs. proximal radius and ulna. | | |

| Study Endpoint | Statistical Model | Estimate of treatment effects |
|--------------------------------|--|--|
| The mean change in flexion of | The data will be analyzed using | ANCOVA: The p-value. |
| the injuired elbow from Week 2 | a) Analysis of Covariance (ANCOVA) | |
| to Week 52 | This model will be used to assess the mean difference in flexion arc between Week 2 and Week 52 among the treatment groups after adjusting for flexion arc at Week 2 (baseline value). The model will have Dependent variable: The flexion arc at Week 52 Independent variable: Treatment group Covariate: Flexion arc at Week 2, sex, age, side of injury is the same as the dominant hand, type of elbow injury, and concurrent injury will be regarded as fixed variables, and site as a random variable. Type of elbow injury is defined as AO/OTA classification, i.e., distal humerus vs. proximal radius and ulna. | Mixed-effect linear regression model: The mean difference and its corresponding 95% confidence intervals |
| | b) Mixed-effects linear regression model This model will be used to account for correlation among observations and estimate the effect of covariates on repeated outcomes. It will use the flexion arc recorded at all time points. Also, the baseline covariates sex, age, side of injury is the same as the dominant hand, type of elbow injury, and concurrent injury will be regarded as fixed variables, and site as a random variable. Type of elbow injury is defined as AO/OTA classification, i.e., distal humerus vs. proximal radius and ulna. | |

| Study Endpoint | Statistical Model | Estimate of treatment effects |
|---|---|--|

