| from Week 2 to Week 52 | a) Analysis of Covariance (ANCOVA) This model will be used to assess the mean difference in OES score between Week 2 and Week 52 among the treatment groups after adjusting for OES score at Week 2 (baseline value). The model will have Dependent variable: The OES score at Week 52 Independent variable: Treatment group Covariate: OES score at Week 2, sex, age, side of injury is the same as the dominant hand, type of elbow injury, and concurrent injury will be regarded as fixed variables, and site as a random variable. Type of elbow injury is defined as AO/OTA classification, i.e., distal humerus vs. proximal radius and ulna. b) Mixed-effects linear regression model This model will be used to account for correlation among observations and estimate the effect of covariates on repeated outcomes. It will use the OES score recorded at the time points. Also, the baseline covariates sex, age, side of injury is the same as the dominant hand, type of elbow injury, and concurrent injury will be regarded as fixed variables, and site as a random variable. Type of elbow injury is defined as | Mixed-effect linear regression model: The mean difference and its corresponding 95% confidence intervals |
| | injury will be regarded as fixed variables, and site as a random variable. Type of elbow injury is defined as AO/OTA classification, i.e., distal humerus vs. proximal radius and ulna. | |

| Study Endpoint | Statistical Model | Estimate of treatment effects |
|---|---|--|
| | Safety | |
| Suspected unexpected Serious Adverse Reaction (SUSAR) up to Week 12 | The analyses will be unadjusted to avoid estimates with wide confidence intervals since we expected that the event rate might be low and that this is likely no event in some treatment groups. | Odds ratio and p-value for both the omnibus and pairwise differences models. |
| | Fisher's exact test The test will be used to compare the proportion of SUSAR up to Week 12 in the treatment groups. If the test produces a significant p-value at α = 0.05, a post-hoc test will be performed to identify groups that | |
| | differ. The p-values will be corrected using the Benjamin- Hochberg FDR method to ensure that the family-wise Type I error remains at 0.05. | |

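### In the Week 2 to Week 52 rows of Table 2 the p-value comes from an ANCOVA and the mean difference with 95% CI from a different all-visit mixed model, so the two describe different quantities and can disagree

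*SAP*

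**What the plan says.** Table 2 in SAP Section 7.2 has eight rows for change from Week 2 to Week 52: flexion-extension arc, flexion, extension, pronation, supination, DASH, PCS and OES. Each lists two models, and the column for treatment-effect estimates divides the output between them: "ANCOVA: The p-value" and "Mixed-effect linear regression model: The mean difference and its corresponding 95% confidence intervals".

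- **Model (a), ANCOVA.** In the flexion-extension row the outcome is one visit: "Dependent variable: The flexion-extension arc at Week 52". The comparison is made "among the treatment groups after adjusting for flexion-extension arc at Week 2 (baseline value"). The PROM rows follow the same pattern, for example "Dependent variable: The OES score at Week 52".
- **Model (b), mixed-effects regression.** Its purpose is to "account for correlation among observations and estimate the effect of covariates on repeated outcomes". On the data used, the SAP says: "It will use the flexion- extension arc recorded at all time points". The listed terms are the baseline covariates and a random site effect. No visit term, treatment-by-visit term, Week 52 contrast or Week 2 covariate is named.

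The trial has three arms: "Ketotifen Fumarate 2 mg, Ketotifen Fumarate 5 mg, or a lactose placebo in a 1:1:1 ratio". The SAP does not say which model leads, or what follows if they point in different directions.

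**The concern.** A p-value and a confidence interval printed for one endpoint are normally two views of one contrast: p falls below 0.05 exactly when the 95% CI excludes zero. Here that link is broken in eight rows. A reader could see p < 0.05 beside an interval that includes zero, or the reverse, with no rule for which result counts. The ANCOVA is the model closest to the endpoint named in the row, yet its adjusted mean difference and CI are not among the planned outputs. With two partly reported models and no leading one, the emphasis can be chosen after the data are seen.

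**Working it through.** **Step 1. The two outputs side by side (flexion-extension row).**

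| Feature | ANCOVA (gives the p-value) | Mixed model (gives the difference and CI) |
|---|---|---|
| Outcome data | Week 52 only | all time points |
| Role of Week 2 | covariate | read literally, one of the outcomes |
| Comparison | across three arms, so apparently a 2-df test | a mean difference, which is pairwise |
| Week 52 contrast | implied by the outcome | not stated |

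No stated figure is at issue. The mismatch follows from the text. In the supination row the mixed model also names the flexion-extension arc, so as written the p-value and the interval would concern different measurements. That is probably a copying slip.

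**Step 2. Comparison with the rest of Table 2.** The secondary Week 12 rows give a mean difference and CI for both the unadjusted and the adjusted model. The safety rows take odds ratio and p-value together. Only the Week 52 rows separate the test from the estimate.

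**Step 3. Size, by formula.** Inputs borrowed from SAP Section 4 for scale: 127 per arm and 11% dropout, so 127 × 0.89 = 113 per arm; a 10 degree effect; SD 25 degrees. Section 4 states these for Week 12, so using them at Week 52 is an assumption. Also assumed: equal within-person correlation ρ between visits, five visits (Weeks 2, 6, 12, 24, 52), an effect growing as 0, 2.5, 5, 7.5, 10 degrees, complete data, and a mixed model read as one treatment effect averaged over visits. With √(2/113) = 0.1330 and ρ = 0.5:

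- ANCOVA: effect 10; SE = 25 × √(1 − 0.5²) × 0.1330 = 2.88; ratio 10/2.88 = 3.47.
- All-visit average: effect (0 + 2.5 + 5 + 7.5 + 10)/5 = 5; SE = 25 × √((1 + 4 × 0.5)/5) × 0.1330 = 2.58; ratio 5/2.58 = 1.94.

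The same data thus give an expected ratio well beyond 1.96 for the p-value and one just under it for the interval. The interval is centred near 5 degrees while the p-value tests a 10 degree difference. The simulation below agrees: 93% of ANCOVA p-values are below 0.05, and 50% of all-visit intervals exclude zero.

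**Step 4. Size, by simulation.** Three arms of 113, 4,000 trials per setting, without baseline covariates or site. The table shows how often the pairwise ANCOVA p-value and the pairwise 95% CI disagree at the 5% level, over ρ = 0.3, 0.5, 0.7.

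| True effect by visit (degrees) | All-visit average | Week 52 contrast, no Week 2 adjustment |
|---|---|---|
| none | 8% to 9% | 3% to 7% |
| 0, 10, 10, 10, 10 | 14% to 21% | 6% to 15% |
| 0, 2.5, 5, 7.5, 10 | 32% to 60% | 6% to 14% |
| 0, 10, 10, 5, 0 | 40% to 62% | 3% to 7% |
| 0, 0, 0, 0, 10 | 74% to 88% | 5% to 14% |

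A two-arm run with 1,500 trials per setting gave 31% to 56% for the growing effect and 9% to 10% with no effect. If the ANCOVA p-value is the three-arm test, set against either pairwise all-visit interval, disagreement runs from 8% to 82% over the same five shapes.

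**Step 5. After the fix.** If one model supplies estimate, CI and p-value for the same contrast, disagreement is 0% by construction.

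**The case against.** Four points can fairly be made for the plan.

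- **Section 7.1 plans estimates.** A reader might infer that no Week 52 effect size can be obtained at all. That goes too far: Section 7.1 promises point estimates with 95% CIs for group differences on continuous endpoints, and Table 1 lists change to Week 52 as an endpoint. An unadjusted difference is therefore arguably planned. It sits under descriptive analysis, however, and is not tied to the ANCOVA. What is missing is the adjusted estimate behind the p-value.
- **The mixed model may be meant to give visit-specific results.** Table 1 asks for changes to Weeks 6, 12, 24 and 52 separately, and the row's endpoint is Week 52. A reader might infer from the growing-effect figures that a third to over half of trials would show contradictory results. The SAP does not support that as a forecast: it gives no time course and no within-person correlation, and it neither states nor excludes a visit-specific contrast. On the Week 52 reading, disagreement is about 3% to 15%. With Week 2 as a covariate and the growing effect averaged over later visits, a run of 2,000 trials per setting gave 4% to 13%. This objection stands against any single headline figure, but the mismatch remains on every reading tried.
- **Table 2 labels each output by its model.** It does not tell the analyst to merge them into one result. That is correct. Still, each model is only half reported, so a row's planned p-value and planned interval come from different analyses whether or not they are printed together.
- **The stakes are limited.** All eight rows are secondary. The primary Week 12 row takes its estimate and CI from one stated model, so nothing here touches the primary result.

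**Conclusion.** The point holds as a reporting and specification fault in eight secondary rows. As written, the p-value and the interval refer to different quantities, and probably to different comparisons (three-arm against pairwise). No ANCOVA-adjusted Week 52 effect is planned, and neither model leads. This rests on the text alone.

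The frequency of disagreement does not. It depends on the assumed correlation (0.3 to 0.7), on the effect's time course and on how the mixed model is read, and is best quoted as a range: about 3% to 15% for a Week 52 contrast; for an all-visit average, 8% to 10% with no effect, 31% to 60% with an effect growing to 10 degrees, and up to 88% with an effect at Week 52 only. The change should be made, but the fault does not threaten the trial's main conclusion.

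**What to change.** For each of the eight rows, choose one of two routes and state it in Table 2:

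1. Report from the ANCOVA the adjusted mean difference, 95% CI and p-value for each dose versus placebo. If a three-arm p-value is also wanted, label it as an omnibus test.
2. Or take all three from a pre-specified Week 52 contrast in one mixed model with a treatment-by-visit term and adjustment for the Week 2 value.

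Name that model as leading. Label the other as supportive and report it with its own estimate, CI and p-value. In the supination row, correct the outcome named for the mixed model.

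The cost is SAP wording. No further data are needed, and route 1 uses numbers the ANCOVA fit already produces.
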